## **21.2 STUDY PERIODS**

### Baseline

The baseline is defined as the day of the first Ozurdex implant injection in the study eye.

The baseline time period is defined as the 3-month period prior to the first Ozurdex injection in the study eye. This 3-month period prior to first Ozurdex injection in the study eye applies to assessments of prior ocular surgical history and treatments, IOP, BCVA, and CRT measures.

### Follow-up period

The period starting the day after the day of the first Ozurdex injection in the study eye is the follow-up period (= post-baseline period). End of follow-up occurs at the last study visit or first receipt of concomitant treatment with anti-VEGF and/or corticosteroids, whichever comes first.

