## **15.0 ANALYSES OF THE OBJECTIVES OF THE STUDY**

### **15.1 ANALYSIS OF THE PRIMARY OBJECTIVE**

The primary objective '*To assess reinjection interval of Ozurdex implants in patients with DME in real-world in Germany and Switzerland*' will be assessed by the following outcomes:

- Total number of Ozurdex reinjections in the study eye during follow-up, and considering years after the first Ozurdex injection in the study eye (See definition in Table 21-1).
- Re[injection interval defined in months as: (Date of injection (j+1) – Date of injection j) ÷ (365.25÷12), for j=1,...,n where n is the number of reinjections in the study eye. The result will be rounded to 0.1.

The number of Ozurdex reinjections in the study eye per year will be first summarized using descriptive statistics for the following parameters:

- The total number and percentage of Ozurdex reinjections received during follow-up.
- Number and percentage (with 95% CI) of patients with at least one Ozurdex reinjection during Year 1 (See definition in Table 21-1), and number of reinjections per patient during Year 1, for all patients in the analysis population. Note: the first Ozurdex injection will not be considered here, only reinjections will be counted.
- Number and percentage (with 95% CI) of patients with at least one Ozurdex reinjection and number of reinjections per patient during Year k (k=2, 3), for patients having a complete Year k of follow-up (see definition of 'Complete year' in Section 21.2).
- Number and percentage of patients receiving each Ozurdex reinjection (first, second, third, etc) for each year of follow-up (Year k, k=1 to 3) considering patients having the complete year of follow-up.

The Ozurdex reinjection interval in the study eye will be described using descriptive statistics for the following parameters:

- Re[injection interval (months) considering all eligible reinjections recorded in the EDC. The 95% CI of the mean will also be presented.
- Re[injection interval (months) considering each reinjection separately (i.e. first reinjection, second reinjection, etc). 95% CI of the mean will also be presented.

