#### **15.2.2 Second Secondary Objective**

The secondary objective '*To describe the reasons for reinjection*' will be assessed considering the primary reason for injection (Disease progression, Lack of effect, Other) reported at each follow-up visit at which an Ozurdex injection was performed in the study eye. The analysis will be summarized using descriptive statistics.

For the study eye, the primary reason for injection (Disease progression, Lack of effect, Other) will be first summarized for each reinjection (i.e. first reinjection, second reinjection, etc.). Then, the primary reason for injection will be described considering all reinjections (the denominator for percentages will be the total number of reinjections in the study eye). Reasons reported as free texts in the 'Other' category will be summarized in a listing.

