### Years after the first Ozurdex injection in the study eye

Years after the first Ozurdex injection in the study eye will be defined as per Table 21-1 below. A patient will be considered to have a complete Year Y of follow-up if the time from the first Ozurdex injection in the study eye to the last follow-up visit is greater or equal to the upper bound of Year Y.

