**Table 21-1 Definition of years after the first Ozurdex injection in the Study eye**

Year # [a]	Year definition [b]
Year 1	Days [2, 365]
Year 2	Days [366, 731]
Year 3	Days [732, 1096]

---

- [a] As per protocol all patients will have at least 1 complete year of follow-up at the site and the maximum number of complete years will be 3. The 1st Ozurdex injection should occur after 1 January 2015 and data will be collected up to 1 September 2018.
- [b] Relative to the date of the first Ozurdex injection in the study eye. Day 1 = the date of the first Ozurdex injection in the study eye. There is no Day 0.

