#### Study duration

The study duration will be derived in months as:

$$(\text{Date of the last follow-up visit} - \text{Date of the first Ozurdex injection in the study eye} + 1) \div (365.25 \div 12). \text{ The result will be rounded to 0.1.}$$

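### Ending follow-up at the first concomitant anti-VEGF or corticosteroid makes the SAP 15.1 total of reinjections leave out every later reinjection

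*SAP*

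**What the plan says.** SAP 21.2 (Follow-up period) starts follow-up on the day after the first study-eye injection and closes it as follows: "End of follow-up occurs at the last study visit or first receipt of concomitant treatment with anti-VEGF and/or corticosteroids, whichever comes first". The sentence does not limit the treatment to the study eye. It is the only place that states when follow-up ends.

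SAP 15.1 uses the term twice for a count under the primary objective: as an outcome, "Total number of Ozurdex reinjections in the study eye during follow-up", and as a summary, "The total number and percentage of Ozurdex reinjections received during follow-up". Neither is exempted from the definition.

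Other rules do not use the cut:

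- **Complete years (SAP 21.2).** The test for completeness reads: "the time from the first Ozurdex injection in the study eye to the last follow-up visit is greater or equal to the upper bound". The bound meant is the last day in that year's window.
- **Table 21-1, footnote [a].** It says that "all patients will have at least 1 complete year of follow-up at the site".
- **Study duration (SAP 21.3.4).** It runs from the first injection to the last follow-up visit.
- **Reasons for reinjection (SAP 15.2.2).** Here "the denominator for percentages will be the total number of reinjections in the study eye", with no end point attached.
- **Protocol section 10.** The study period runs to 1 September 2018.
- **Interval summary (SAP 15.1).** It is made "considering all eligible reinjections recorded in the EDC"; which reinjections are eligible is not defined.

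SAP 22.0, which lists departures from the protocol, does not mention the cut.

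**The concern.** The total is meant to describe how often Ozurdex is given in practice. A programmer who follows SAP 21.2 would stop counting at the first added anti-VEGF or corticosteroid, even when the patient goes on receiving Ozurdex. The count would be too low and could disagree with two other outputs of the same study: the yearly counts and the denominator for reasons for reinjection.

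A comparison is also at risk. SAP 6.3 plans a subgroup by concomitant anti-VEGF and/or corticosteroid in the study eye, Yes versus No. A cut at study-eye treatment can lower the total only among the Yes patients. Fewer reinjections with concomitant treatment could then appear simply because counting stopped.

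**Working it through.** **1. The plan's own figure.** The only design figure for the primary objective is the precision of the mean interval in SAP 19.0, 1.96 × SD / √150. It reproduces: 1.96 × 1.5 / √150 = 0.240 and 1.96 × 3.0 / √150 = 0.480, which round to the stated 0.2 and 0.5 months. It concerns the interval, not the count. The documents give no expected total.

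**2. One patient under the SAP's rules.** Spacing is 4.8 months, a mean cited in SAP 19.0: 4.8 × 30.4375 = 146.1 days. With Day 1 as the first injection, reinjections fall on days 147, 293, 439 and 585. Assume a first study-eye anti-VEGF on day 120 and a last follow-up visit on day 800.

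| Output | Rule | Count |
|---|---|---|
| Year 1 | days 2–365 | 2 (147, 293) |
| Year 2 | days 366–731, complete because 800 ≥ 731 | 2 (439, 585) |
| Reasons denominator (15.2.2) | all study-eye reinjections | 4 |
| Total during follow-up (15.1) | ends on day 120 | 0 |

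Inclusion requires two implants, so a patient with no reinjection should not exist. Under SAP 13.0, treatment on the day of the first injection also counts as concomitant, so such a patient's follow-up would end before it began.

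**3. Cohort, simple formula.** Assume regular intervals of m months, F months observed, a proportion q of patients treated at a time uniform over F, and Ozurdex continued. A reinjection at time t is omitted for a treated patient with probability t/F, so

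share omitted = q × (mean reinjection time) / F.

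For m = 6.7, F = 24 and q = 0.30, reinjections fall at 6.7, 13.4 and 20.1 months, with mean 13.4. The share is 0.30 × 13.4/24 = 0.1675. In 150 patients, 450 reinjections become 450 × 0.8325 ≈ 375, and 150 × 0.30 × 6.7/24 ≈ 12.6 patients show zero. Across m = 4.7 or 6.7 and F = 12, 24 or 36, the share is 5.2–5.9% for q = 10%, 15.7–17.6% for 30% and 26.1–29.4% for 50%.

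**4. Cohort, simulation (60,000 patients per scenario).** Intervals are gamma, 4.8 ± 1.8 or 6.7 ± 2.3 months (Protocol 14.1), with a minimum of 1 month and at least one reinjection per patient. Variance is split equally between and within patients (assumed). Observation is uniform over 12–44 months, or over 32–44 months because selection starts closest to 1 January 2015 (Protocol 9.2). Treatment timing is independent of the intervals (assumed). Ranges span the four combinations.

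| Timing of first concomitant treatment | 10% treated | 30% treated | 50% treated |
|---|---|---|---|
| Uniform, Ozurdex continued | 5.2–5.4% | 15.7–16.5% | 26.2–27.7% |
| First third of observation, continued | 8.8–9.2% | 26.3–27.5% | 43.9–45.7% |
| Last third of observation, continued | 1.7–1.9% | 5.3–5.5% | 8.8–9.1% |
| Uniform, half of treated patients stop Ozurdex | 2.7–2.9% | 8.6–9.1% | 15.1–16.0% |
| All treated patients stop Ozurdex | 0 | 0 | 0 |

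**5. Within the Yes/No subgroup.** If Ozurdex continues, the Yes group loses 52–55% of its reinjections (uniform timing), 88–91% (first third) or 18–19% (last third), whatever the treatment rate. The No group loses none by construction. With uniform timing and 12–44 months observed, the Yes mean falls from 5.8 to 2.7 at 4.8 ± 1.8 months while the No mean stays at 5.8. At 6.7 ± 2.3 months it falls from 4.0 to 1.8 while the No mean stays at 4.0.

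**The case against.** The strongest reply is that the SAP does not use the term consistently. SAP 15.1 itself sends the reader to the complete-year rule, which runs to the last follow-up visit, so a sensible team might never apply the cut to this total. That is possible. But the rule that would have to be ignored is the only stated end of follow-up, and the second end point confirms the conflict without resolving it.

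The cut could also be a deliberate description of Ozurdex-only use. No text says so for this total. Protocol 14.2.1 treats Ozurdex-only as a possible patient group, and SAP 13.1 counts concomitant treatments per patient, which needs observation past the first one.

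Several points stand and limit the concern:

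- The total is a descriptive addition by the SAP. Protocol 14.2.2.2 plans yearly counts and intervals.
- The derived variables in SAP 21.3.1 are restricted to the study eye, so the missing eye in SAP 21.2 may be only a wording gap.
- The header of Table 6-1 is damaged in the text available. That the Yes/No subgroup applies to the primary objective is inferred from five marked columns and five listed subgroups.
- An uncut total need not equal the yearly sum, because Years 2 and 3 are restricted to completers and Table 21-1 stops at day 1096. These restrictions can only make the yearly sum smaller, so a total below that sum would still point to the cut.
- The percentages follow from assumed rates and timings, and the worked patient is an extreme case.

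**Conclusion.** The concern holds. As written, SAP 21.2 and SAP 15.1 together give a count of reinjections that can be too low and can contradict other outputs of the same plan. This is a rule that yields a wrong count, not merely missing detail.

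Its true size is unknown. In the scenarios above it runs from nil, if Ozurdex stops with the added treatment, to just under half of all reinjections, if half the patients are treated early and continue. The subgroup distortion would be larger, provided that subgroup is reported for the primary objective.

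The conclusion does not extend to the yearly counts, which use fixed day windows. Nor is bias shown in the interval mean, although the undefined eligibility of reinjections leaves open whether the cut reaches it. The point should be fixed before analysis.

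**What to change.** - In SAP 15.1, count all study-eye Ozurdex reinjections up to the last follow-up visit, with data to 1 September 2018. This is the end point already used for complete years and study duration.
- Define eligible reinjections for the interval summary in the same way, and state that the Table 21-1 windows are not cut at concomitant treatment.
- If the cut is kept for other outputs, such as the follow-up summaries in SAP 12.2, 12.3 and 15.2.1, or as an Ozurdex-only sensitivity analysis of the counts, limit it to study-eye treatment and name the outputs it governs. End the numerator and the time at risk together, and note that this censoring may be informative.

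The cost is SAP wording and one programming definition. No new data are needed.

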### Years after the first Ozurdex injection in the study eye

Years after the first Ozurdex injection in the study eye will be defined as per Table 21-1 below. A patient will be considered to have a complete Year Y of follow-up if the time from the first Ozurdex injection in the study eye to the last follow-up visit is greater or equal to the upper bound of Year Y.

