### **14.2.2.2 Primary Objective**

Number of patients with at least one reinjection and number of reinjections per patient during the year following the first Ozurdex implant injection will be summarized descriptively for all patients from the Analysis population. For patients with more than one year of follow-up, number of patients with at least one reinjection and number of reinjections per patient during the follow-up year considered will be described for each year of follow-up (e.g. 2nd year of follow-up, 3rd year of follow-up...). The number and percentage of patients receiving each injection (first, second, etc.) will be presented for each year of follow-up.

Time between Ozurdex implant injections will be summarized overall and for each reinjection, i.e. first reinjection, second reinjection...

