### Study design

[figure not shown]
Study CMO-MA-EYE-0564 is a retrospective, non-interventional, observational, multi-center, drug utilization study to be conducted in adult patients with visual impairment due to DME treated with Ozurdex implants in Germany and Switzerland from 1 January 2015 to 1 September 2018. Data from approximately 150 patients will be collected by retrospective review of medical charts; including up to 50 patients that are naïve of any anti-VEGF treatment before their first Ozurdex implant injection. Sites will be hospital-based experienced medical retina centers treating DME patients.

[figure not shown]
Patients' medical charts will be selected over a 4-month period at each site or until the study target population has been reached. Site personnel will be invited to complete a screening log with all patients who received their first Ozurdex implant injection from 1 January 2015 until 1 September 2017 to help them identify eligible patients. For each patient, retrospective data on the study eye will be abstracted from existing medical records from time of first Ozurdex implant injection until 1 September 2018. Data abstraction will cover at least one year of follow-up after first Ozurdex injection for all selected patients. The study eye will be defined as the eye that received the most Ozurdex injections. Key relevant data will also be collected on the contralateral eye.

Consent from patients will not be requested; as the study is retrospective and anonymized, a waiver of consent will have been requested from the Ethics Committees.

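### Year 2 and Year 3 reinjection percentages count only patients whose last visit reaches the end of that year, so in routine-care charts the denominator can depend on whether the eye is still being treated

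*SAP*

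**What the plan says.** SAP 15.1 assesses the primary objective through two outcomes: the number of reinjections (in total and by year) and the reinjection interval.

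- For Years 2 and 3, the percentage with at least one reinjection and the number per patient are given "for patients having a complete Year k of follow-up". The percentage receiving each successive reinjection is given by year, "considering patients having the complete year of follow-up".
- SAP 21.2 treats a year as complete if the time from first injection "to the last follow-up visit is greater or equal to the upper bound of Year Y". Table 21-1 puts the upper bounds at Day 731 (Year 2) and Day 1096 (Year 3).
- The total number of reinjections during follow-up has no complete-year condition. Nor does the interval, which is described "considering all eligible reinjections recorded in the EDC".
- SAP 21.2 (Follow-up period) ends follow-up at the last visit or at the first concomitant anti-VEGF or corticosteroid, whichever is earlier. The complete-year rule looks at the last visit only.
- Protocol 14.2.2.2 introduces the later-year counts with "For patients with more than one year of follow-up, number of patients with at least one reinjection". It does not say how a partly observed year is handled.

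**The concern.** The data are abstracted from routine charts, and Protocol 15.3 requires no study visits. An eye reinjected at the site after Day 731 has a visit after Day 731 and so has a complete Year 2 automatically. An eye that has stopped implants qualifies only if the patient returns for another reason. The last visit is thus partly a consequence of treatment, and conditioning on it can select eyes that are still being treated.

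The administrative cut-off has no such link to the outcome. It is the same date for everyone: "data will be collected up to 1 September 2018". Together with the first-injection date it fixes which patients could have completed Year 2 or 3.

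At stake is whether the Year 2 and 3 percentages describe the treated population or mainly eyes still in care. The SAP plans no sensitivity analysis that would tell the reader which.

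**Working it through.** **1. Calendar inputs.** First injections fall within the window for "patients who received their first Ozurdex implant injection from 1 January 2015 until 1 September 2017", which is 974 days. Possible follow-up to 1 September 2018 therefore runs from 365 to 1339 days. Since 1339 ≥ 1096 and 1339 < 4 × 365.25 = 1461, the SAP's statement that "the maximum number of complete years will be 3" reproduces. A complete Year 2 needs a first injection by 31 August 2016 (731 days before the cut-off). A complete Year 3 needs one by 1 September 2015 (1096 days before).

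**2. Eye-time left out of the per-year tables.** Assume entry uniform over the window, no loss, and n = 150.

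- Complete Year 2: (1339 − 731)/974 = 608/974 = 62%, about 94 patients.
- Complete Year 3: (1339 − 1096)/974 = 243/974 = 25%, about 37 patients.
- Year 2 eye-years used: 93.6 × 366/365.25 = 93.8. Partial: 150 × 366/974 = 56.4 patients × 183/365.25 = 28.2. Left out: 28.2/122.1 = 23%.
- Year 3 eye-years used: 37.4 × 365/365.25 = 37.4. Partial: 150 × 365/974 = 56.2 patients × 182.5/365.25 = 28.1. Left out: 28.1/65.5 = 43%.
- Years 2 and 3 together: (28.2 + 28.1)/(122.1 + 65.5) = 56.3/187.6 = 30%.

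The documents give neither an entry distribution nor a loss rate, so these were varied:

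| Entry | Loss per year after month 12 | Years 2+3 left out |
|---|---|---|
| Uniform | 0 | 30% |
| Uniform | 0.1 / 0.2 / 0.3 | 33% / 37% / 40% |
| Earliest half of window | 0 | 18% |
| Earliest half of window | 0.1 to 0.3 | 21% to 28% |
| Earliest quarter of window | 0 | about 0% |

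Protocol 9.2 selects patients with the earliest first injections first, which pushes the share down.

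**3. When the percentage is biased.** Let π be the true proportion reinjected in the year. Let r1 and r0 be the probabilities of counting as complete for reinjected and non-reinjected eyes. The rule estimates

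π·r1 / (π·r1 + (1 − π)·r0),

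so the estimated odds are the true odds times r1/r0. There is no bias if r1 = r0, and overstatement if r1 > r0.

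**4. Size, by simulation.** All inputs are assumptions: intervals of 5 ± 2 months, a 10% chance that each reinjection is the last, a mean of 8 months from last implant to leaving, and uniform entry. Only patients with at least two implants and 12 months at the site are kept, as the inclusion criteria require. The comparator is all such patients whose Year k ended by the cut-off. Figures are good to about one point.

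| Stoppers who leave | Year 2: rule v all | Year 3: rule v all |
|---|---|---|
| Half | 88 v 85 | 75 v 66 |
| All | 97 v 88 | 96 v 68 |

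The implied r1/r0 in Year 2 is (88/12)/(85/15) = 1.3 if half leave and (97/3)/(88/12) = 4.4 if all do. In a second model (stopping at 0.3 per year after the second injection), departures unrelated to stopping gave 78.1 against a true 78.4, which is no material bias.

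**5. The opposite direction.** Suppose implants after a switch to anti-VEGF or corticosteroid are not counted, because 21.2 has ended follow-up, while the eye stays in the denominator because visits continue. In the second model, with half of stoppers leaving and switch rates of 0.1 to 0.4 per year, the Year 2 figure is 80.5 down to 63.6 against about 81.

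**The case against.** The strongest reply is that the study is descriptive with no hypothesis (Protocol 6), the restricted denominator is stated openly, and SAP 8.0 reports last-visit dates and study duration. The rule uses the last visit, not the last implant. Protocol 10.6 and 10.8.1 record the contralateral eye at visits, so patients may keep attending after the study eye stops. Putting partial years straight into the percentage would err the other way: with no departures the second model gave 71.4 against a true 78.4. All of this stands. It is why the planned table should be kept and why the bias is conditional.

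Four stronger readings are tempting, and the documents do not support them.

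- **The percentages are overstated.** The documents give no stopping rate, no leaving rate and no link between them.
- **A third of later follow-up is thrown away.** About 34% results only with uniform entry and with time after Day 1096 counted, although that time belongs to no defined year. The loss touches only the per-year tables.
- **The Year 2 gap is 14 points or more.** Under the first model's assumptions, the comparator falls to about 81 to 83 only if patients with under 12 months of follow-up are included. They are ineligible. With the criterion applied it is about 97 against 88.
- **The SAP departs from the protocol without saying so.** Protocol 14.2.2.2 is silent on partial years, and the SAP introduces itself as a more detailed elaboration. Settling the point in the SAP is not clearly a change that had to be listed in SAP 22.0.

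**Conclusion.** The concern holds in conditional form. The Year 2 and 3 denominators depend on the last chart visit, which can depend on whether the eye is still receiving implants. If stoppers tend to leave, the percentages are too high: in the scenarios run, by about 3 to 9 points in Year 2 and 9 to 28 points in Year 3, from half to all of stoppers leaving. If leaving is unrelated to stopping, the cost is precision only. If implants after a switch go uncounted while the eye remains in the denominator, the percentages can be too low. A reader of the planned table could not tell which applies.

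The interval, which is the stated primary objective and the basis of the sample size, is not restricted by this rule, so the point does not undermine it. Every size given here rests on assumed entry, stopping, leaving and switching patterns.

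**What to change.** Keep the complete-year table and add two lines.

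1. **Cut-off denominator.** Give the same Year 2 and Year 3 percentages for all Analysis Population patients whose first injection was early enough for Year k to end by 1 September 2018, whatever their last visit. Count leavers as not reinjected. Label the result a lower bound, since implants given elsewhere are unseen.
2. **Reinjection rate per patient-year over all follow-up.** State one end-of-follow-up definition and apply it to both events and person-time, so that a switch of therapy is handled alike in each. Present this as a gain in precision. It does not correct for informative leaving: if every stopper leaves, the first model gives 2.03 per year against a true 1.85.

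The cost is one supplementary table and a footnote on care elsewhere. Injection and visit dates are already collected, so no new data are needed.
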